4. PATIENT SELECTION AND RESTRICTIONS

Investigators should keep a record ie, patient screening log, of patients who entered pre-study screening.

Each patient must meet all of the inclusion criteria and none of the exclusion criteria for this study at the time of starting study treatment. Under no circumstances can there be exceptions to this rule.

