4.2 Exclusion criteria

Patients must not enter the study if any of the following exclusion criteria are fulfilled

- 1. Treatment with any of the following:
 - Treatment with an EGFR TKI (eg, erlotinib or gefitinib) within 8 days or approximately 5x half-life, whichever is the longer, of the first dose of study treatment. (If sufficient wash-out time has not occurred due to schedule or PK properties, an alternative appropriate wash-out time based on known duration and time to reversibility of drug related adverse events could be agreed upon by AstraZeneca and the Investigator)
 - Any cytotoxic chemotherapy, investigational agents or anticancer drugs for the treatment of advanced NSCLC from a previous treatment regimen or clinical study within 14 days of the first dose of study treatment.
 - AZD9291 in the present study (ie, dosing with AZD9291 previously initiated in this study)
 - Major surgery (excluding placement of vascular access) within 4 weeks of the first dose of study treatment
 - Radiotherapy with a limited field of radiation for palliation within 1 week of the first dose of study treatment, with the exception of patients receiving radiation to

more than 30% of the bone marrow or with a wide field of radiation which must be completed within 4 weeks of the first dose of study treatment

- Patients currently receiving (or unable to stop use at least 1 week prior to receiving the first dose of AZD9291) medications or herbal supplements known to be potent inhibitors of CYP2C8 and potent inhibitors or inducers of CYP3A4 (Appendix H)
- 2. Any unresolved toxicities from prior therapy greater than Common Terminology Criteria for Adverse Events (CTCAE) grade 1 at the time of starting study treatment with the exception of alopecia and grade 2, prior platinum-therapy related neuropathy
- 3. Spinal cord compression or brain metastases unless asymptomatic, stable and not requiring steroids for at least 4 weeks prior to start of study treatment
- 4. Any evidence of severe or uncontrolled systemic diseases, including uncontrolled hypertension and active bleeding diatheses, which in the investigator's opinion makes it undesirable for the patient to participate in the trial or which would jeopardise compliance with the protocol, or active infection including hepatitis B, hepatitis C and human immunodeficiency virus (HIV). Screening for chronic conditions is not required
- 5. Any of the following cardiac criteria:

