- 12. Judgment by the investigator that the patient should not participate in the study if the patient is unlikely to comply with study procedures, restrictions and requirements

In addition, the following is considered a criterion for exclusion from the exploratory genetic research:

- 13. Previous allogenic bone marrow transplant
- 14. Non-leukocyte depleted whole blood transfusion within 120 days of the date of the genetic sample collection

4.3 **Restrictions**

The following restrictions apply while the patient is receiving study treatment and for the specified times before and after:

- 1. Females of child-bearing potential should use reliable methods of contraception from the time of screening until *3 months* after discontinuing study treatment. Acceptable methods of contraception include abstinence, tubal ligation, oral or transdermal contraceptives, copper-banded intra-uterine devices and vasectomised partner. All hormonal methods of contraception should be used in combination with the use of a condom by their male sexual partner for intercourse.
- 2. Male patients should be asked to-use barrier contraceptives (ie, by use of condoms) during sex with all partners during the trial and for a washout period of 3 months. Patients should avoid procreation for *6 months* after completion of trial treatment. Patients should refrain from donating sperm from the start of dosing until *6 months* after discontinuing study treatment. If male patients wish to father children they should be advised to arrange for freezing of sperm samples prior to the start of study treatment.
- 3. All patients must try to avoid concomitant use of medications, herbal supplements and/or ingestion of foods with known potent inducer/inhibitory effects on CYP3A4 and/ or CYP2C8 whenever feasible, but patients may receive any medication that is clinically indicated for treatment of adverse events. Such drugs must have been discontinued for an appropriate period before they enter screening and for a period of *3 months* after the last dose of AZD9291. All concomitant medications should be captured on the eCRF. Guidance on medicines to avoid, medications that require close monitoring and on washout periods is to be provided.

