Appendix H Guidance regarding Potential Interactions With Concomitant Medications

TABLE OF CONTENTS

PAGE

	TABLE OF CONTENTS	.2
1.	DRUGS INHIBITING CYP3A4 OR CYP2C8 METABOLISM THAT ASTRAZENECA STRONGLY RECOMMEND ARE NOT COMBINED WITH AZD9291	3
2.	DRUGS INDUCING CYP3A4 METABOLISM THAT ASTRAZENECA STRONGLY RECOMMEND ARE NOT COMBINED WITH AZD9291	.4
3.	MEDICINES WHOSE EXPOSURES MAY BE AFFECTED BY AZD9291 THAT ASTRAZENECA CONSIDERS MAY BE ALLOWED WITH CAUTION	.4
4.	DRUGS THAT MAY PROLONG QT INTERVAL	.5
4.1	Drugs known to prolong QT interval	.5
4.2	Drugs that may possibly prolong QT interval	.5

LIST OF TABLES

Table 1	Drugs inhibiting CYP3A4 or CYP2C8	.3
Table 2	Drugs inducing CYP3A4	.4
Table 3	Exposure, pharmacological action and toxicity may be increased by AZD9291	.4
Table 4	Drugs prolonging QT interval	.5
Table 5	Drugs that may prolong QT interval	.6

GUIDANCE REGARDING POTENTIAL INTERACTIONS WITH CONCOMITANT MEDICATIONS

The use of any natural/herbal products or other "folk remedies" should be discouraged, but use of these products, as well as use of all vitamins, nutritional supplements, and all other concomitant medications must be recorded in the eCRF.

AZD9291 is an investigational drug for which no data on in vivo interactions are currently available. Based on in vitro data and predicted clinical exposure data, AZD9291 is considered unlikely to cause clinically significant drug interactions through inhibition or induction of cytochrome P450 enzyme activity. In vitro data have shown that the principal CYP enzymes responsible for the Phase I metabolism of AZD9291 are CYP2C8 and CYP 3A4.

1. DRUGS INHIBITING CYP3A4 OR CYP2C8 METABOLISM THAT ASTRAZENECA STRONGLY RECOMMEND ARE NOT COMBINED WITH AZD9291

The contribution of Phase I metabolism to the total clearance of AZD9291 is currently unknown but, to ensure patient safety, the following potent inhibitors of CYP2C8 and CYP3A4 must not be used during this study for any patient receiving AZD9291.

Table 1Drugs inhibiting CYP3A4 or CYP2C8

Contraindicated drugs	Withdrawal period prior to AZD9291 start
Clarithromycin, telithromycin, troleandomycin	1 week
Gemfibrozil	
Indinavir, lopinavir, nelfinavir, ritonavir, saquinavir, tipranavir, telaprevir	
Itraconazole, ketoconazole, posaconazole, voriconazole	
Mibefradil	
Nefadozone	

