This list is not intended to be exhaustive, and a similar restriction will apply to other agents that are known to strongly modulate CYP3A4 or CYP2C8 activity. Appropriate medical judgment is required. Please contact AstraZeneca with any queries you have on this issue.

2.

Table 2

DRUGS INDUCING CYP3A4 METABOLISM THAT ASTRAZENECA STRONGLY RECOMMEND ARE NOT **COMBINED WITH AZD9291**

Contraindicated drugs	Withdrawal period prior to AZD9291 start
Carbamazepine, phenobarbital, phenytoin	3 weeks
Rifampicin, rifabutin, rifapentin	
St John's Wort	
Phenobarbitone	5 weeks

Drugs inducing CYP3A4

This list is not intended to be exhaustive, and a similar restriction will apply to other agents that are known to strongly modulate CYP3A4 activity. Appropriate medical judgment is required. Please contact AstraZeneca with any queries you have on this issue.

3. **MEDICINES WHOSE EXPOSURES MAY BE AFFECTED BY AZD9291 THAT ASTRAZENECA CONSIDERS MAY BE ALLOWED WITH CAUTION**

Table 3 Exposure, pharmacological action and toxicity may be increased by AZD9291

Warning of possible interaction	Advice	
Alfentanil	Drugs are permitted but caution should be	
Amodiaquine	exercised and patients monitored closely for possible drug interactions. Please refer to full prescribing information for all drugs prior to co- administration with AZD9291.	
Repaglinide		
Sirolimus		
Tacrolimus		
Torsemide		
All statins		

There are currently no data confirming that there is a pharmacokinetic (PK) interaction between these agents and AZD9291; in vitro data suggests AZD9291 has the potential to cause drug interactions at the intestinal level through CYP3A4, it has also been shown to be an inhibitor of CYP2C8, and a weak inhibitor of OATP_{1B1}. The potential for AZD9291 to inhibit other transporter systems is currently unknown. This list is not intended to be exhaustive, and a similar restriction will apply to other agents that are known to depend on CYP3A4, CYP2C8 and/or transporter proteins for metabolism. Appropriate medical judgement is required. Please contact AstraZeneca with any queries you have on this issue

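### Exclusion 1 allows a 1-week washout for potent CYP3A4 inducers, but Appendix H Table 2, which it cites, requires 3 weeks (5 for phenobarbitone)

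*Protocol*

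**What the plan says.** The last item of exclusion 1 (Section 4.2) reads "Patients currently receiving (or unable to stop use at least 1 week prior to receiving the first dose of AZD9291" and names potent CYP2C8 inhibitors, potent CYP3A4 inhibitors and potent CYP3A4 inducers together, with a reference to Appendix H. Section 4 says of the selection criteria: "Under no circumstances can there be exceptions to this rule".

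Appendix H gives withdrawal periods in two tables, each under the column heading "Withdrawal period prior to AZD9291 start":

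- Table 1 (inhibitors) opens with the row "Clarithromycin, telithromycin, troleandomycin" at 1 week.
- Table 2 (inducers) gives 3 weeks on the row "Carbamazepine, phenobarbital, phenytoin" and 5 weeks for phenobarbitone.

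Section 4.3, item 3, adds "Such drugs must have been discontinued for an appropriate period before they enter screening", gives no length, and says: "Guidance on medicines to avoid, medications that require close monitoring and on washout periods is to be provided". Section 5.3.2 repeats the first of these statements and names Appendix H as the place where washout periods are given.

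The EGFR-TKI item of exclusion 1 is built differently. Its period is "within 8 days or approximately 5x half-life, whichever is the longer, of the first dose of study treatment".

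**The concern.** The figure in exclusion 1 is the inhibitor period applied to inducers as well. Because the criteria allow no exceptions, that figure decides eligibility, and for inducers it is shorter than the period the same protocol prescribes.

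Section 2.3 names CYP3A4 as a principal enzyme in the human metabolism of AZD9291. Enzyme induction that persists into the dosing period could therefore lower early plasma concentrations. Pharmacokinetics is a secondary objective (Section 1.2), and the concentrations feed the population PK analysis (Section 7.5.1).

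**Working it through.** **Step 1. Compare the periods.** All are counted to the first dose of AZD9291, so a different reference date does not explain the gap.

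| Drug class | Exclusion 1 | Appendix H | Difference |
|---|---|---|---|
| Potent CYP3A4/CYP2C8 inhibitors | 1 week | 1 week (Table 1) | 0 |
| Potent CYP3A4 inducers | 1 week | 3 weeks (Table 2) | 3 − 1 = 2 weeks |
| Phenobarbitone | 1 week | 5 weeks (Table 2) | 5 − 1 = 4 weeks |

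In the text copy available, 3 weeks is printed only on the carbamazepine, phenobarbital and phenytoin row. I read the rifamycin and St John's Wort rows as sharing that cell, because Table 1 likewise prints its period on the first row only. If they do not share it, the mismatch still holds for the drugs with a printed period.

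**Step 2. Who passes the criterion but is inside the Table 2 period?** Let *s* be the days from stopping the inducer to first dose. Exclusion 1 admits *s* ≥ 7. Table 2 asks for *s* ≥ 21, or *s* ≥ 35. The conflict is *s* = 7 to 20 for 3-week inducers and *s* = 7 to 34 for phenobarbitone.

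**Step 3. Which assessments fall inside?** A sample is inside the period if *s* + (its day after first dose) is below 21, or below 35. Sampling days come from Section 6.6.1, Table 5.

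*Expansion and extension* (first dose = Cycle 1 Day 1):

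| Assessment | Days since stop if *s* = 7 | Inside 3-week period | Inside 5-week period |
|---|---|---|---|
| Cycle 1 Day 8 | 7 + 7 = 14 | *s* = 7 to 13 | *s* = 7 to 27 |
| Cycle 1 Day 15 | 7 + 14 = 21 | never | *s* = 7 to 20 |
| Cycle 2 Day 1 | 7 + 21 = 28 | never | *s* = 7 to 13 |
| First scan, week 6 ± 7 days | 42 to 56 | never | never |

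*Escalation* (first dose = Cycle 0 Day 1; 7 ± 2 days to multiple dosing, Section 3.1), *s* = 7:

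| Assessment | Days since stop (gap 5/6/7/8/9 days) | Inside 3-week period | Inside 5-week period |
|---|---|---|---|
| Cycle 0 Day 1 to Day 6 | 7 to 12 | yes | yes |
| Cycle 1 Day 1 pre-dose | 12/13/14/15/16 | yes | yes |
| Cycle 1 Day 8 | 19/20/21/22/23 | gap 5 or 6 only | yes |
| Cycle 1 Day 15 | 26/27/28/29/30 | no | yes |
| Cycle 2 Day 1 | 33/34/35/36/37 | no | gap 5 or 6 only |

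**Step 4. Does other text close the gap?**

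- Section 4.3, item 3, sets no length.
- Section 5.3.2 sends the reader to Appendix H for washout periods, which favours Table 2 over the 1-week figure.
- The appended amendment revises Appendix H Tables 1 and 3 and refers back to Table 2. As shown, it changes neither Table 2 nor exclusion 1.

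**Step 5. Is Table 2 consistent with itself?** It is not. Phenobarbital and phenobarbitone are two names for one drug, listed at 3 and at 5 weeks.

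**The case against.** The strongest reply is that the texts can all be followed at once. One week is a minimum, exclusion 1 cites Appendix H in the same sentence, and Sections 4.3 and 5.3.2 require an appropriate washout before screening. If the Table 2 period were counted to screening entry (day −28 to −1), the drug would have to stop 21 + 1 = 22 to 21 + 28 = 49 days before first dose, and the 7-to-20-day patient would not comply. The heading over Table 2 is also phrased as a strong recommendation, so a firm 1-week floor with a longer advised period is a conceivable design.

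It is true that a site following Table 2 breaches nothing. But the criterion still admits a patient whom Table 2 would hold back. The Appendix H reference follows the drug classes and reads as a pointer to a drug list. Where the authors wanted a longer alternative to govern, in the EGFR-TKI item, they wrote it out. Table 2 labels its drugs contraindicated and counts to the start of AZD9291, not to screening.

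The objection that the practical effect is small stands. The number of patients on inducers is not given, and Appendix H says the contribution of Phase I metabolism to clearance is unknown. The wider effect in escalation is largely past: by 19 November 2013 doses of 20 to 240 mg had been given with no dose-limiting toxicity reported in the evaluation period, and 80 mg had been selected (Section 5.2).

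**Conclusion.** The concern holds. For potent CYP3A4 inducers, exclusion 1 is 2 weeks shorter than the protocol's own withdrawal period, and 4 weeks shorter for phenobarbitone.

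The consequence is limited to early exposure and consistent eligibility. In expansion and extension, a 3-week inducer can affect one post-dose PK sample, and only for stops 7 to 13 days before dosing. The 5-week entry can reach the Cycle 2 Day 1 profile. ORR precision and sample size do not change, and the first scan falls outside both periods. The benefit is mainly for patients still to enrol.

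Two assumptions apply. The Table 2 periods are taken as limits, since the protocol does not say induction ends on that day. The size of any fall in exposure is unknown. The point merits correction at the next amendment.

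**What to change.** Reword the item in exclusion 1 along these lines:

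> Potent inhibitors of CYP3A4 or CYP2C8 (Appendix H Table 1) not stopped at least 1 week before the first dose, or potent inducers of CYP3A4 (Appendix H Table 2) not stopped at least 3 weeks before it (5 weeks for phenobarbital/phenobarbitone).

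In Table 2, list phenobarbital/phenobarbitone once, at the longer period or at the one the sponsor confirms. In Section 4.3, item 3, refer to exclusion 1 for the pre-dose period.

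A lighter option is to keep 1 week and add that the Appendix H period applies if longer, as the EGFR-TKI item does. Table 2 must still be corrected first.

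The cost is wording in an amendment, with no added procedure or sample. A patient on an inducer waits 2 more weeks, or 4 for phenobarbital. This is a real cost in patients who have just progressed and for whom the entry requirement is a life expectancy of only 12 weeks. It may become the limiting washout, since exclusion 1 asks 14 days for chemotherapy and 8 days or about five half-lives for an EGFR TKI. Three weeks (21 days) fits the 28-day screening window. Five weeks (35 days) does not, so that stop must begin before screening.

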4.3.1 Concomitant treatments

Information on any treatment in the 4 weeks prior to starting study treatment and all concomitant treatments given during the study, with reasons for the treatment, will be recorded in the Case Report Form (CRF). After permanent discontinuation of AZD9291 and 28 day follow up, only subsequent regimens of anti-cancer therapy will be recorded in CRF. If medically feasible, patients taking regular medication, with the exception of potent inhibitors or inducers of CYP3A4 and inhibitors of CYP2C8 (see Section 4.2 exclusion 1, and Appendix H), should be maintained on it throughout the study period. Patients taking concomitant medications whose disposition is dependent upon intestinal CYP3A4 and/or transporter proteins and/or CYP2C8 and

which have a narrow therapeutic index should be closely monitored for signs of changed tolerability as a result of increased exposure of the concomitant medication whilst receiving AZD9291. Guidance on medications that require close monitoring is given in Appendix H.

Other anticancer agents, investigational agents and radiotherapy should not be given while the patient is on study treatment.

Pre-medication will be allowed after, but not before the first dose of study treatment. This includes management of diarrhoea, nausea and vomiting.

Blood transfusions are allowed at any time during the study.

Granulocyte colony stimulating factors should not be used prophylactically during Cycle 1. Use of prophylactic colony stimulating factors may be considered after Cycle 1 following discussion with the AstraZeneca Study Team Physician.

Patients may receive treatment with corticosteroids and/or bisphosphonates for the treatment of bone metastases. Patients may also receive radiotherapy for painful bony metastases.

Supportive care and other medications that are considered necessary for the patient's well-being, may be given at the discretion of the investigator.

5. STUDY TREATMENT AND CONDUCT

5.1 Treatment

AZD9291 is planned to be administered orally as a single daily dose (although alternative frequencies or intermittent schedules may be instigated in response to emerging safety, tolerability or PK data).

AstraZeneca will supply AZD9291 as capsules or tablets for oral dosing. Additional information about the investigational product may be found in the Investigators' Brochure.

Investigational product	Dosage form and strength	Manufacturer
AZD9291	20 mg and 40 mg Capsule	AstraZeneca
AZD9291	40mg and 80mg Tablet	AstraZeneca

Capsules and tablets will be packed in high-density polyethylene (HDPE) bottles with childresistant closures. One or more bottles of AZD9291 will be dispensed at each dispensing visit depending on the dose. Bottles will be dispensed to subjects in the AstraZeneca packing provided. The packaging includes bottles, caps and a label. Bottle tampers should not be broken prior to dispensing study drug to a patient. For the Ph II extension cohort an IVRS/IWRS system will be deployed to manage the supply of AZD9291 tablets to sites and to manage the dispensing of AZD9291 to patients. All patients entering the extension cohort will be dispensed the tablet formulation. All other cohorts of patients will continue to be dispensed the capsule formulation.

Labels will be prepared in accordance with Good Manufacturing Practice and local regulatory guidelines. The labels will fulfil Good Manufacturing Practice Annex 13 requirements for labelling. Label text will be translated into local language.

The label will include the Name of the Sponsor, Study Code, For Clinical trial use only and /or any other market specific requirements

All study drugs should be kept in a secure place under appropriate storage conditions. The investigational product label on the pack specifies the appropriate storage.

Patients (with the exception of patients with insulin dependent diabetes) must fast for ≥ 1 hours prior to taking a dose to ≥ 2 hour post dose. Water is permitted during this fasting period.

Patients will be required to fast (water only) for at least 8 hours prior to the collection of a fasting glucose sample as per the study plan, (see Table 2, Table 3 and Table 4).

5.1.1 Starting dose, dose escalation scheme and stopping criteria

Dosing will begin at 20mg once daily.

A cycle of study treatment will be defined as 21 days of continuous dosing.

In the first cohort, a delay of at least 7 days will be mandatory between the administration of the first (single) dose to the first patient and administration of first (single) dose to subsequent patients. Providing there are no serious or unexplained safety issues, dosing of the remainder of the cohort will continue as suitable patients are identified. However, should ambiguous findings occur, the SRC may choose to stagger the start of dosing for the remainder of the cohort of patients. Providing there are no safety concerns after completion of the first cohort, subsequent cohorts of patients will be dosed as suitable patients are identified. If ambiguous findings occur after the first cohort the SRC may choose to stagger dosing in the second cohort and likewise for subsequent cohorts.

Patients will be enrolled to ensure a minimum of 3 and a maximum of 6 evaluable patients per cohort. Dose escalation and de-escalation will follow the scheme below, according to the following logic:

• If no dose-limiting toxicity (DLT) is observed (for definition see Section 5.1.3) in a cohort of 3-6 evaluable patients then dose escalation may occur. Dose increases will be permitted after review of data from a minimum of 3 evaluable patients has been performed.

Table 1

- If one patient experiences a DLT in a group of 3 or more evaluable patients then the cohort will be expanded to include 6 evaluable patients. If only one DLT is observed in the complete cohort of 6 evaluable patients then dose escalation may occur.
- If 2 or more patients experience a DLT in a group of up to 6 patients, irrespective of the number of patients enrolled, the dose will be considered not tolerated and recruitment to the cohort and dose escalation will cease. A lower intermediary dose (de-escalation) may be considered in order to better define the MTD.

Prior to achieving MTD, dose escalation will stop if:

- Delivery of the next dose level would require dosing of >8 capsules or tablets per single administration, or
- There is evidence in the dose-exposure relationship of saturation of absorption.

See Table 1 below for the proposed dose escalation scheme. All dose levels beyond cohort 1 may change in light of emerging safety and pharmacokinetic data. The planned dose escalations will not exceed doubling of the dose in principle. However up to a quadrupling of dosing may be permitted in the first two escalations only, if the drug concentrations from the first or second dose level are not measureable or are deemed to be far from predicted drug exposure (eg, greater than 2-fold difference) and there have been no significant safety or tolerability issues.

Cohort	Dose mg (to be administered once daily)	
1	20	
2	40	
3	80	
4	160	
5	200	
Х	XXX	

Proposed	dose	escalation	scheme
----------	------	------------	--------

There will be a minimum of 2 days between conduct of the last patient assessment required for SRC review from one cohort and the start of dosing in the subsequent cohort.

There will be no intra-patient dose escalations with the exception of patients who were started and have remained on treatment at a dose lower than 80mg for at least 6 months, have shown clinical benefit (as judged by the investigator) and have then developed RECIST confirmed disease progression. The escalated dose must be agreed in advance between the Investigator and AZ Study Physician, and will not exceed 80mg; which has been declared safe and tolerable by the SRC.

The dose for subsequent cohorts or a decision to stop recruitment to the escalation phase of the study will be agreed by the SRC after review of the data from each cohort (see Section 5.1.5).

